6. OBJECTIVES

6.1. Primary objective

To assess the efficacy of GMRx2 compared to placebo for lowering BP in adults with hypertension.

6.2. Secondary objectives

[figure not shown]
To assess the safety of GMRx2 compared to placebo for the treatment of hypertension in adults.

To assess the longer-term efficacy and safety of GMRx2 in the optional Open-Label Extension Period.

7. TRIAL DESIGN

An international randomized, double-blind, placebo-controlled, parallel-group trial with a 2-week pre-randomization placebo run-in, a 4-week randomized treatment period and a 4-week safety follow-up period or an optional Open-Label Extension period. The overall study design is shown in Figure 3 and 4.

Figure 2: Study design summary

GMRx2 Dose1 = T 10 / A1.25 / I 0.625; GMRx2 Dose2 = T 20 / A 2.5 / I 1.25; T=telmisartan; A=amlodipine; I=indapamide; R = randomization; RI = Run-in; FU = Follow-up. For participants entering the optional open-label extension period, this will begin after week 4 and replace Period 3

7.1. Trial Design Rationale

This trial is designed to investigate the efficacy and safety of GMRx2 for reducing BP in adult participants with high BP compared to placebo, i.e. the full effects of GMRx2 compared to no BP-lowering medications. The run-in period will assess participant's adherence to taking medication and completing trial procedures and therefore will enhance the power of the trial to detect difference between GMRx2 and placebo. The double-blind period will assess the efficacy and safety of GMRx2 dose 1 and GMRx2 dose 2 compared to placebo. Double-blinding will avoid any performance bias by investigators and trial participants. The safety follow-up period will assess safety over a 30-day period after discontinuation of the trial medication. The optional Open-Label Extension Period will assess efficacy and tolerability over a one-year period.

7.2. Sub-studies

Participants will be invited to provide venous blood and urine specimens at baseline, 4 weeks and if applicable at 8 weeks visits for use in planned substudy analyses. These samples will be analysed for renal biomarkers⁶⁰ and drug metabolite levels.^{61, 62} The samples will be immediately processed and stored at $-80^{\circ}\text{C} \pm 10^{\circ}\text{C}$ and shipped during or at the end of the study to designated central laboratories for storage until analyses have been completed. In addition, some centers will participate in a sub-study of ambulatory BP measurement and provide participants the option of joining this substudy.

8. METHODS: PARTICIPANTS, INTERVENTION & OUTCOMES

8.1. Trial Setting & Participant Recruitment

Trial participants will be recruited from clinics or hospital-based out-patient departments or primary care centers that provide hypertension care in the participating countries. Based on the recruitment rate and trial timelines, other modes of recruitment that could be used include community resources particularly to target women and minority/under-served populations (also to ensure adequate representation of these groups), referrals from other hospitals/clinics, and trial recruitment advertisement in the form of poster or flyer, via social media etc.

8.2. Participant Eligibility

The guiding principle of participant eligibility is patients with hypertension who could appropriately be treated with GMRx2 dose version 1 or GMRx2 dose version 2 or placebo.

8.2.1. Inclusion Criteria

At screening visit

1. Provided signed consent to participate in the trial.
2. Adult aged ≥ 18 years.
3. Low calculated CV risk according to local guidelines such that pharmacological BP-lowering treatment is not mandatory: e.g. Pooled Cohorts Equation 10-years ASCVD risk $<10\%$ in the USA.
4. Likely diagnosis of hypertension, defined as one or more of:
 - automated SBP at this clinic visit according to trial methods (see Appendix 2) of ≥ 130 mmHg on no BP lowering medicines or ≥ 120 mmHg on 1 BP lowering medicine that will be stopped at this visit, OR
 - documentation in last 6 months of office SBP ≥ 140 mmHg and/or DBP ≥ 90 mmHg on no BP lowering medicines or SBP ≥ 130 mmHg and/or DBP ≥ 85 mmHg on 1 BP lowering medicine that will be stopped at this visit, OR
 - documentation in last 6 months of home SBP ≥ 130 mmHg and/or DBP ≥ 80 mmHg on no BP lowering medicines or SBP ≥ 120 mmHg and/or DBP ≥ 75 mmHg on 1 BP lowering medicine that will be stopped at this visit, OR
 - documentation in last 6 months of ambulatory daytime SBP ≥ 130 mmHg and/or DBP ≥ 80 mmHg on no BP lowering medicines or SBP ≥ 120 mmHg and/or DBP ≥ 75 mmHg on 1 BP lowering medicine that will be stopped at this visit
5. No contraindication to trial medications, including 2-weeks placebo run-in and 4-weeks randomized treatment period with GMRx2 (dose version 1 or 2) or placebo.

At randomization visit

1. Home seated mean SBP 130-154 mmHg in the week before the randomization visit.
2. Adherence of 80-120% to placebo run-in.
3. Tolerated placebo run-in.
4. Adherence to home BP monitoring schedule: in the week before randomization, at least 6 measures (e.g. ≥ 2 sets of triplicate measures) including at least 1 morning and 1 evening each with ≥ 2 measures. Morning is defined as any measure in the am and evening as any measure in the pm. Morning and evening do not have to be same day.

At week 4 (for optional Open-Label Extension Period)

1. Provided signed informed consent.
2. Completed randomized treatment and willing to continue GMRx2-based treatment regimen for 12 months.

8.2.2. Exclusion Criteria

At screening visit

1. Receiving 2 or more BP-lowering drugs. Note: A single tablet containing 2 or 3 different BP lowering agents (i.e. a combination medication) is considered as 2 or 3 BP lowering drugs, respectively.
2. Clinic seated mean SBP \geq 160 mmHg and/or DBP \geq 100 mmHg.
3. Meets any criteria of local ethical or regulatory requirements related to severe acute respiratory syndrome coronavirus-2 (SARS-CoV-2) that would deem participation in a clinical trial unsuitable.
4. Contraindication, including hypersensitivity (e.g. anaphylaxis or angioedema), to the placebo run-in treatment or to any of the trial medications in the three randomized groups.
5. Current/history of transient ischemic attack, stroke, or hypertensive encephalopathy.
6. Current/history of acute coronary syndrome, unstable angina, myocardial infarction, percutaneous transluminal coronary revascularization, or coronary artery bypass graft
7. Current atrial fibrillation. Patients with a history of paroxysmal atrial fibrillation are potentially eligible as long as there has been no episode in the last 3 months, while patients with a history of persistent or permanent atrial fibrillation are not eligible.
8. Current/history of New York Heart Association class III and IV congestive heart failure
9. Current/history of cardiomyopathy or any other cardiovascular condition of sufficient severity to contraindicate the trial medications or require a contraindicated medication.
10. Current/history of a known secondary cause of hypertension, such as primary aldosteronism, renal artery stenosis, pheochromocytoma, or Cushing's syndrome.
11. Current/history of severe uncontrolled diabetes (HbA1c $>$ 11.0% ($>$ 97 mmol/mol)) within the last three months.
12. Current/history of end-stage renal disease or anuria.
13. Current concomitant illness or physical impairment or mental condition that in the judgment of the investigator could interfere with the effective conduct of the trial or constitutes a significant risk to the participants' safety or well-being.
14. Arm circumference that is too large or too small for available cuffs to allow accurate measurement of BP. Upper limit is 55cm in all countries, while lower limit is 15cm or 24cm in different countries, depending on available cuff sizes.
15. Currently taking or might need during the trial, a concomitant treatment which is known to interact significantly with the trial medication: digoxin, lithium, diabetics receiving aliskiren, moderate and strong CYP3A4 inhibitors (e.g. ritonavir, ketoconazole, diltiazem], simvastatin $>$ 20 mg/day, immunosuppressants.
16. Might need treatment with drugs that are prohibited during the trial: other antihypertensive drugs, endothelin receptor antagonists, neprilysin inhibitors, or other drugs that may affect BP (see Appendix 5).
17. Current surgical or medical condition that might significantly alter the absorption, distribution, metabolism, or excretion of trial drugs such as prior major gastrointestinal tract surgery (e.g. gastrectomy, lap band, or bowel resection) or acute flare of inflammatory bowel disease within one year.
18. Individuals working $>$ 2-night shifts per week.
19. Participated in any investigational drug or device trial within the previous 30 days. This does not include participants in the extended safety follow-up portion of a trial.
20. History of alcohol or drug abuse within 12 months.

At randomization visit

1. Unable to adhere to the trial procedures during the run-in period.
2. Any of the following which in the investigator's judgment may compromise the safety or wellbeing of the participant if randomized to the trial medications:
 - a. High or low clinic BP levels even in the light of the values for home BP that are available for that participant. The exact levels of BP are not specified, since there is clinical uncertainty as to

the relevance of BP levels which are high/low in clinic only; for example, the clinical relevance of 'whitecoat hypertension' is uncertain.

[figure not shown]
- b. High or low home DBP levels. The exact levels of DBP are not specified, reflecting clinical uncertainty of the implications of isolated diastolic hypertension. However, home DBP values of >99 mmHg may typically be considered as requiring treatment intensification, and such participants would not be suitable for randomization.
3. Pregnant or had a positive pregnancy test or unwilling to undertake a pregnancy test during the trial and up to 30 days after the discontinuation of the trial medication or breastfeeding or of childbearing age and not using an acceptable method of contraception (defined in the Manual of Procedures). Acceptable methods of birth control include hormonal prescription oral contraceptives, contraceptive injections, contraceptive patch, intrauterine device, double-barrier method (e.g. condoms, diaphragm, or cervical cap with spermicidal foam, cream, or gel), or male partner sterilization. Contraception should be used for at least 1 month before the Randomization visit and until the end of trial participation.
4. Current estimated glomerular filtration rate (eGFR) <60 ml/min/1.73m.²
5. Electrolyte levels that would be regarded as contraindications for any of the potential treatment arms e.g. serum sodium <132mmol/l or >148 mmol/l or serum potassium <3.1 mmol/l or >5.6mmol/l.
6. Current/history of aspartate aminotransferase (AST) or alanine aminotransferase (ALT) >3 times the upper limit of normal range within 6 months.
7. Any abnormal laboratory value which in the judgment of the investigator could interfere with the effective conduct of the trial or constitutes a significant risk to the participants' safety or well-being.
8. Fulfilling any of the exclusion criteria mentioned for the screening visit, when verified again at the randomization visit.

At week 4 (for optional Open-Label Extension Period)

1. Contraindication to open-label GMRx2-based BP-lowering treatment.

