8.4.3. Optional Open-Label Extension Period

In a subset of sites, participants who are still receiving study medication at Week 4 will be invited to continue on to an optional Open-Label Extension Period with the aim to assess effectiveness, safety and adherence over a 52-week period. Willing participants will enter the Open-Label Extension Period at the Week 4 visit, at which time they will be allocated open-label GMRx2-Dose version 1. Follow-up visits will be conducted at Week 6, 8, 16, 28, 40, and end of Open-Label Extension Period visit at week 52 (See Table 6). Participants will continue to monitor BP at home, once per week until the Week 8 visit, and thereafter on a set day every month (e.g. 1st day of the month) until the week 52 visit. Home BP measurements will be made using a validated, electronic, automatic, digital upper-arm cuff and recorded in a home BP diary, as specified in the Blood Pressure Monitoring Manual of Procedures. During follow-up visits, if home BP from the most recent measurement is above 130 mm Hg for SBP and/or above 80 mmHg for DBP, BP-lowering therapy will be up-titrated in the following order: GMRx2-Dose1 → GMRx2-Dose2 → GMRx2-Dose3 (telmisartan 40mg/amlodipine 5mg/indapamide 2.5mg) → GMRx2-Dose3 plus telmisartan 40 mg/amlodipine 5 mg → GMRx2-Dose3 plus telmisartan 40 mg/amlodipine 5 mg plus spironolactone 25 mg. The rationale for this regimen is based on the evidence indicating that:

- About 80% of the maximum BP-lowering effects of BP-lowering regimens are achieved by 2 weeks⁵⁰
- US hypertension guidelines recommend a home BP target of <130/80 mmHg²⁵
- Up-titration steps should provide clinically meaningful BP reductions – the BP reductions of only 2-3/1-2 mmHg achieved by increasing the dose of a single drug are likely to be only modestly effective and such steps can act as barriers to effectively achieving BP goals.⁵⁰ Doubling the dose of telmisartan 40 mg/amlodipine 5 mg achieves an additional 5/4 mmHg reduction,⁵¹ and the use of concomitant ARB therapy reduces the incidence of pedal oedema associated with higher dose amlodipine.^{59,61} The Pathway-2 trial demonstrated that a mineralocorticoid receptor antagonist is superior to a beta-blocker or an alpha-blocker in patients not controlled on maximal doses of three drugs.⁶²

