10. PARTICIPANT TIMELINE & ASSESSMENTS

10.1. Schedule of Evaluations

Table 5 outlines the trial visits schedule and assessments for participants in the trial who do not enter the optional Open-Label extension period; for those who do enter the Open-Label Extension period, **Table 6** outlines the visits schedule from Week 4 onwards. It should be noted that there is flexibility in the timing of blood and urine collection tests before randomization as noted in **Table 5**, to suit participant preferences and local clinic feasibility and ease of scheduling, with the proviso that all of the requirements for eligibility at Screening and Randomization are met, as outlined in Section 8.2.

Table 5: Trial visits schedule and assessments: Randomization and Safety Follow-up Periods

Visit Name	PRE-SCREEN (Optional)	SCREEN (Run-in start)	RAND (Run-in end)	FU1 (End of trial medication)	EOT ⁵ (Telephone safety FU)
Visit Week	Week -4	Week -2		Week 4	Week 8
Visit Day (Visit window days)	-28	-14 (-12 to -21)*		28 (±7)*	56 (±7)*
Written informed consent ¹	✓	✓			
Eligibility (inclusion & exclusion)	✓	✓	✓		
Medical history	✓	✓			
Physical examination ²		✓			
Demographics		✓			
Anthropometrics – Height, weight		✓			
Clinic BP, standing BP, pulse		✓	✓	✓	
12-lead electrocardiogram (ECG)		✓			
Cardiovascular risk assessment		✓			
Dispensing of home BP monitor		✓			
Home BP monitoring				→	
Home BP monitor brought to clinic			✓	✓	
24-hour ambulatory BP measurement if participating in substudy				✓	
Blood Collection					
Study bloods ³		✓		✓	
Follow-up creatinine with eGFR ⁴					✓ ⁴
Pregnancy test if childbearing potential		✓			
Blood sample for storage for substudy		✓		✓	
Urine Collection³					
Albumin-creatinine ratio		✓		✓	✓ ⁴
Urine sample for storage for substudy		✓		✓	✓ ⁴
Medications					
Discontinue BP lowering medication (if applicable)	✓	✓			
Dispensation of run-in medication		✓			
Allocation of randomized trial medication			✓		
Dispensation of trial medication			✓		
Return of trial medication			✓	✓	
Adherence to trial medication			✓	✓	
Review of concomitant medications	✓	✓	✓	✓	✓
Safety					
AESI or SAE					→

¹ At Screening visit, if not collected previously. Written informed consent may be collected at pre-screening.

² Systems-based examination deemed necessary for the safety of participants by the site investigator

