Table 6: Trial visits schedule and assessments for participants in Open-Label Extension Period

Visit Name	Commence Open-Label Extension	OLE FU1	OLE FU2	OLE FU3	OLE FU4	OLE FU5	OLE EOT
Visit Week	Week 4	Week 6	Week 8	Week 16	Week 28	Week 40	Week 52
Visit window days	(±7)	(±7)	(±7)	(±14)	(±14)	(±14)	(±14)
Written informed consent	✓						
Eligibility for open-label period	✓						
Clinic BP, standing BP, pulse		✓	✓	✓	✓	✓	✓
Home BP monitoring							►
Home BP monitor brought to clinic		✓	✓	✓	✓	✓	✓
Blood Collection*							
Fasting glucose							✓
Fasting lipid profile ¹							✓
Sodium, potassium, chloride			✓	✓			✓
Creatinine with eGFR			✓	✓			✓
Uric acid							✓
Urine Collection*							
Albumin-creatinine ratio				✓ ²			✓
Urine sample for storage for substudy				✓ ²			
Medications							
Dispensation of trial medication	✓	✓	✓	✓	✓	✓	
Return of trial medication		✓	✓	✓	✓	✓	✓
Adherence to trial medication		✓	✓	✓	✓	✓	✓
Review of concomitant medications		✓	✓	✓	✓	✓	✓
Safety							
AESI or SAE							►

¹ Total cholesterol, low-density lipoprotein cholesterol, high-density lipoprotein cholesterol

² At Week 8, only for participants who have had ≥30% reduction in eGFR and/or ≥30% increase in serum creatinine between baseline and Week 4 visits

* All laboratory investigations will be performed at the trial site based local laboratory. Local practice can be followed whether the blood draws are done before, at or following each clinic visit. Any other investigations at discretion of site investigator
EOT=End of trial; FU=Follow up

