10.3.2. Screening Visit

- Assess the potential participant's interest and eligibility for the trial.
- Discuss the trial with the potential participant, including using the PISCF, and obtain signed informed consent. This can also be done before the screening visit. The potential participant can be given the opportunity to consider information and return within the time window for randomization.
- Collect demographic information.
- Collect information on medical history, perform a physical examination.
- Review all medication currently being taken.
- Measure height and weight.
- Measure BP and pulse.

- Perform 12-lead ECG.
- Collect blood and urine samples, including for pregnancy, (if applicable) or arrange for these tests to be completed during the run-in period. Results must be reviewed and eligibility confirmed prior to randomization, but are not required for review prior to the beginning of the placebo run-in.
- Collect sub-study blood and urine samples (if applicable) – these can also be collected during run-in or at the randomization visit if preferred.
- Assess eligibility as per the trial inclusion and exclusion criteria.
- Consider stopping current BP monotherapy to facilitate trial eligibility, if clinically appropriate and considered safe. Informed consent must be obtained before the modification of medication. If medication is altered, a period of at least 14 days is required between alteration of BP treatment and trial randomization (ie the minimum placebo run-in duration is 14 days). In situations in which it is not deemed clinically appropriate to stop BP monotherapy for the trial duration, such participants should be regarded as ineligible.
- Demonstrate home BP measurement and dispense home BP monitor (record serial number) to participant.
- Dispense run-in medication as soon as possible.

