10.3.9. Week 4 Commence Open-Label Extension Period (selected sites only)

- Obtain consent for Open-Label Extension Period
- Switch from randomized treatment to Open-Label GMRx2 Dose1, as outlined in 8.4.3, page 22.

- For a device will be collected and new BP monitor will be issued

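### Pregnancy is tested once, before randomization; no test is scheduled before open-label GMRx2 starts at Week 4 or at any extension visit

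*Protocol*

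**What the plan says.** Randomization exclusion 3 (Protocol 8.2.2) covers participants who are pregnant, have tested positive, or are "unwilling to undertake a pregnancy test during the trial and up to 30 days after the discontinuation of the trial medication". It also requires contraception from a month before randomization until participation ends.

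The Table 5 row "Pregnancy test if childbearing potential" (Protocol 10.1) has one tick, under Screening. SAP Appendix 2 repeats it. Protocol 10.3.2 gives some latitude on timing: "Collect blood and urine samples, including for pregnancy, (if applicable) or arrange for these tests to be completed during the run-in period". Eligibility must be confirmed from the results before randomization.

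At Week 4, 10.3.7 collects blood and urine, but the itemized test list in footnote 3 of Table 5 has no pregnancy test. For those entering the extension, 8.4.3 says "at which time they will be allocated open-label GMRx2-Dose version 1" and 10.3.9 says "Switch from randomized treatment to Open-Label GMRx2 Dose1". Neither mentions a test.

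In Table 6 the row "Dispensation of trial medication" is ticked at Weeks 4, 6, 8, 16, 28 and 40, and "Eligibility for open-label period" is ticked at Week 4. A footnote adds "Any other investigations at discretion of site investigator". There is no pregnancy row, and 10.3.10 and 10.3.11 name no test.

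Pregnancy is a reason for the investigator to stop medication (8.8). It must be reported if it occurs at any time from consent to 30 days after stopping (17.2.5).

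**The concern.** The plan treats pregnancy as incompatible with trial drug: it excludes at entry, stops treatment and triggers a report. After randomization, the stopping and reporting rules work only if someone learns of the pregnancy, and the schedule contains no step designed to find one.

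The gap matters most at Week 4. Most participants who had been on placebo would first take active drug then, relying on a test that is already weeks old. Extension participants can afterwards be titrated up to GMRx2 Dose 3 plus telmisartan 40 mg/amlodipine 5 mg plus spironolactone 25 mg (8.4.3), still with no scheduled check. Routine safety questioning does not fill the gap, because sites ask about AESIs and SAEs (17.2.3) and pregnancy is not on the AESI list (17.1.2).

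What is at stake is participant safety. No endpoint or efficacy analysis depends on it.

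**Working it through.** The plan gives no figure to reproduce here. The check is a count of scheduled tests, followed by calendar arithmetic.

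**Scheduled tests against drug supply** (Protocol Tables 5 and 6, 10.3.2 to 10.3.11; SAP Appendix 2)

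| Time point | Drug supplied | Pregnancy test scheduled |
|---|---|---|
| Screening or run-in | Placebo | 1 |
| Randomization | Randomized drug | None new; earlier result reviewed |
| Week 4, extension entry | Open-label Dose 1 | 0 |
| Weeks 6, 8, 16, 28, 40 (extension) | Open-label regimen | 0 |
| Week 52 (extension) | None; drug stopped | 0 |
| Week 8 call (not in extension) | None | 0; no pregnancy question |
| After Week 52 | None | 0; AESI/SAE self-report for 14 days |

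Scheduled tests after randomization: 0. Open-label dispensings (Weeks 4, 6, 8, 16, 28, 40): 6.

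**Age of the last scheduled test at extension entry**

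Inputs from Table 5: Screening at Day -14 (window -12 to -21) and Week 4 at Day 28 (±7).

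- Test at the end of run-in: 0 + 28 = 28 days.
- Test at nominal Screening: 14 + 28 = 42 days.
- At the visit-window limits: 0 + 21 = 21 days and 21 + 35 = 56 days.

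The 56 days is not a true maximum. Protocol 10.3.1 allows blood tests to be arranged after consent at pre-screening, and 10.3.3 allows laboratory results up to 30 days old to be reused at re-screening.

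**Age at Week 52** (Table 6: Day 364, ±14)

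- Nominal: 0 + 364 = 364 days to 14 + 364 = 378 days.
- At the window limits: 0 + 350 = 350 days to 21 + 378 = 399 days, with the same caveat on the upper figure.

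**Untested treatment time in the extension**

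52 - 4 = 48 weeks by visit numbering. Protocol 8.4.3 speaks of 52 weeks and the synopsis of 12 months; on that reading the interval is longer.

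**Ceiling on former placebo participants**

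SAP 2.6.1 gives 295 randomized. If the 2:2:1 ratio held, 295 × 1/5 = 59 were on placebo. This includes men, those not of childbearing potential, sites without the extension, and those who declined it or had stopped medication. The documents do not allow it to be reduced further.

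**Coverage after the last dose**

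- Week 8 call: 56 - 28 = 28 days after the Week 4 visit, or 49 - 35 = 14 to 63 - 21 = 42 days at the window limits.
- After Week 52: 14 days of self-report (10.3.11) against a 30-day pregnancy reporting window (17.2.5), so 30 - 14 = 16 days are not covered.

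**Spacing under the proposed tests**

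Tests at Weeks 4, 8, 16, 28, 40 and 52 leave gaps of 4, 8, 12, 12 and 12 weeks.

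**The case against.** The strongest reply is that no rule is broken. Exclusion 3 asks about willingness to take a test and orders no series of them, so how often to test is a design preference. That stands. A reader might infer that the schedule contradicts the criterion; the wording does not support that.

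There are also real controls: contraception until participation ends, an eligibility and contraindication check at Week 4, and freedom for the site to order any test. They reduce the risk, but none is a scheduled means of detection. Contraception was also required before randomization, and the plan still scheduled a test there. A contraindication check with no test can miss an unrecognized pregnancy, and discretionary testing may differ across the planned 25 to 30 sites.

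The Manual of Procedures, cited in 8.2.2 for contraception methods, and the extension consent form were not available. Either could call for tests, so the statement is limited to the Protocol and SAP.

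Three further inferences go too far:

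- That every former placebo participant first meets active drug at Week 4. Protocol 8.6 allows add-on telmisartan 40 mg and/or amlodipine 5 mg during the randomized period.
- That all follow-up ends at Week 52. Protocol 10.3.11 requests AESI/SAE reports for 14 more days, and 17.2.3 requires SAEs that the site learns of to be recorded until 30 days after stopping. Neither is a pregnancy check.
- That 59 people are at risk. That number is only a loose ceiling.

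**Conclusion.** The point holds as an inexpensive patient-safety improvement that the sponsor should make. The Protocol and SAP schedule one pregnancy test, before randomization, and none before open-label drug is dispensed at Week 4 or during the extension. At extension entry that test is nominally 28 to 42 days old, and older if earlier laboratory results were reused. About 48 weeks of treatment follow without a scheduled check.

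This rests on the visit numbering in Tables 5 and 6 and on the Manual of Procedures not already requiring tests. The documents do not give the number of participants of childbearing potential or the number entering the extension, so expected pregnancies cannot be estimated. The case for testing within the extension and at its start is firm; the exact frequency, and the form of the check after the last dose, are more open to judgment.

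**What to change.** For participants of childbearing potential:

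1. Add a pregnancy test at Week 4 to Table 5, SAP Appendix 2 and Protocol 10.3.7 and 10.3.9, with the result reviewed before extension drug is dispensed.
2. Add a pregnancy-test row to Table 6, and matching lines to 10.3.10 and 10.3.11, at existing visits. Weeks 8, 16, 28, 40 and 52 would keep the longest gap at 12 weeks; the sponsor may choose another frequency.
3. Add a pregnancy question to the existing Week 8 call (10.3.8).
4. Add pregnancy to the self-report request after Week 52 (10.3.11) and extend it from 14 to 30 days, to match 17.2.5.

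If the Manual of Procedures already requires these tests, a cross-reference in Tables 5 and 6 is enough for items 1 and 2.

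The cost is a few simple tests in a subset at visits that already take place, one question on an existing call, a longer self-report period, and an amendment that must go to ethics committees and regulators (18.4) with sites planned in five countries. Because 295 participants were already randomized (SAP 2.6.1), the benefit goes to anyone still in or entering the extension and to future use of this protocol.
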